1.3 Schedule of Activities

| Procedures | Pre-screening (Pre-consent) | Visit(s) 1 | Visits 2-10 | Visit 11 | Visits 12-15 |
|----------------------------------|--------------------------------|------------|-------------|----------|--------------|
| Eligibility Questionnaire Review | X | X | - | - | - |
| Informed Consent | - | X | - | - | - |
| Demographics | X | X | - | - | - |
| Clinical history | X | X | - | - | - |
| Nursing Eval | - | X | - | X | X |
| Outcome Evaluation | - | - | - | - | - |
| MRI scan | - | X | - | X | - |
| Questionnaires | - | X | - | X | X |
| MBSR training | - | - | X | - | - |
| Adverse Events Reporting | - | X | X | X | X |

Abbreviated Title: Mindfulness and Teen Vaping

Version Date: 07/21/2025

NIH IRB#: IRB001855

| TABLE 1. DIAGNOSTIC MEASURES AND ASSESSMENT BATTERY | | Visit #* | | | |
|--|--|-----------------|--------------|------------|---------------|
| DOMAIN | INSTRUMENT(S) | #1 | #2-10 | #11 | #12-15 |
| Diagnostic Assessment | Mini International Neuropsychiatric Interview for Children and Adolescents-DSM-5.0 version (MINI-KID-5) or SCID-RV | X | | | |
| Demographics and Puberty | Demographics questionnaire and Pubertal Development Scale | X | | | |
| MRI Safety | MRI Safety Assessment | X | | X | |
| Substance Use Measures | General Substance Use: Timeline Follow-back (TLFB) - 28 Days (V1), 7 Days (V12-15): tobacco vaping (vaping days and vapes or puffs/day), tobacco smoking, cannabis, alcohol, other drugs; Substance Use History Questionnaire; Cannabis Use Disorder Test (CUDIT); Craving Questionnaire | X | | | X |
| | E-Cigarette Measures (Vapers only): E-Cigarette Dependence Scale (EDS, 4 items); Modified Fagerstrom Test for Nicotine Dependence (FTND); Nicotine Social Influence Questionnaire (NSIQ) | X | | | X |
| | Biospecimens: Urine Cotinine Test, Urine Drug test (UDT), Breath CO and ALC tests | X | | X | X |
| Psychological Measures | Sensitivity to Reward and Sensitivity to Punishment Questionnaire (SRSPQ), Patient Health Questionnaire-9 (PHQ-9), General Anxiety Disorder-7 (GAD-7), Difficulty in Emotion Regulation Scale, 5-trial Adjusting Delay Discounting Task (bench), Momentary Impulsivity Scale | X | | | X |
| Mindfulness Measures | Five-Facet Mindfulness Questionnaire (FFMQ), Mindfulness Practice Questionnaire (MPQ) (Visits #3-15 only) | X | X (MPQ only) | | X |
| Cognitive Measures | Digit Span (DGS) assessment (forward and backwards) | X | | | X |

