***Note:** Visit(s) 1 = Baseline Assessment and MRI scan 1 but may be split into two to four visits (some of which may be conducted virtually) ~0-3 months pre-MBSR intervention; Visits 2-10 = MBSR training; Visit 11 = MRI scan 2 ~0-6 weeks post-MBSR intervention; Visits 12-15 (starting within about 3 weeks post-MBSR training) = monthly follow-up visits (preferably in-person but virtual, if need be); Visit 11 may be combined with Visit 12 or 13 or done separately.

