3 OBJECTIVES AND ENDPOINTS

| OBJECTIVES | ENDPOINTS | JUSTIFICATION FOR ENDPOINTS |
|--|---|---|
| Primary | | |
| (1) To characterize static and dynamic rsFC differences in hippocampal networks related to nicotine vaping in adolescents. | (1) Seed-based s-rsFC between hippocampal seed regions and large-scale brain networks (DMN, ECN, SN) and d-rsFC measures comparing time in state and state transition probabilities between N=40 nicotine vaping and N=40 non-vaping youth. | (1) Hippocampal networks are related to nicotine exposure, especially in adolescence. |
| (2) To characterize rsFC changes (Δ rsFC) in hippocampal networks and d-rsFC following a technology-delivered MBSR program in nicotine vaping adolescents. | (2) Seed-based s-rsFC analysis between hippocampal seed regions and large-scale brain networks (DMN, ECN, SN) and d-rsFC measures (time in state and state transition probabilities) within the frequent nicotine | (2) Hippocampal connectivity and d-rsFC measures are related to both nicotine exposure and MBSR training. |

Abbreviated Title: Mindfulness and Teen Vaping

Version Date: 07/21/2025

NIH IRB#: IRB001855

| | | |
|---|--|---|
| | vaping group Pre/Post MBSR. | |
| Secondary | | |
| (1) To assess engagement with a smoking cessation app and changes in various behaviors following MBSR training. | (1) Engagement with apps and Δ scores for each behavioral measure (e.g., vaping behavior, emotion regulation, cognitive function) in the within-subject analyses of adolescents who vape, undergoing MBSR training. | (1) Understanding feasibility and acceptability as well as efficacy is important in assessing potential for development of MBSR training as a new therapeutic intervention for vaping-related TUD in youth. |
| (2) To assess other imaging metrics such as resting connectivity from alternative sites related to mindfulness meditation and nicotine dependence (e.g., dACC) between vaping and non-vaping teens and pre-/post-MBSR training in vaping teens. | (2) Connectivity metrics. | (2) These metrics will provide a fuller understanding of teen vaping and the effects of MBSR training. |

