4 STUDY DESIGN

4.1 Overall Design

This is natural history study (comparison of vaping to non-vaping adolescents) and an open label pilot study (MBSR intervention to vaping adolescents).

This single-sight study will be carried out at the NIDA-IRP's Biomedical Research Center in Baltimore, MD.

The study will enroll up to 60 nicotine vaping youth and 60 non-vaping youth to obtain complete data on N=40 tobacco vaping youth 13-18 years old and N=40 age, sex, race/ethnicity, SES matched typically developing (TD) non-vaping/non-smoking youth. The study intervention, given to vaping teens, is a Mindfulness-Based Stress Reduction (MBSR) training. The intervention is a group-based instructor-led mindfulness-based stress reduction (MBSR) training.

Abbreviated Title: Mindfulness and Teen Vaping

Version Date: 07/21/2025

NIH IRB#: IRB001855

The MBSR intervention will consist of eight weekly 2-hour sessions and one 3-hour retreat that will take place at the NIDA BRC. Each group will consist of 8-12 participants.

Participants will be recruited online and via our concurrent vaping survey study. Only nicotine vaping youth will participate in the MBSR intervention. The vaping group will participate in one to four primary data gathering visits, all but one of which can be done virtually. The visit that will include the first MRI scan visit must take place in-person 0-3 months pre-MBSR intervention, and the second MRI scan visit will take place 0-6 weeks post-MBSR intervention. The TD non-vaping group will not participate in the MBSR intervention, and therefore will only participate in the baseline assessments (one to four virtual or in-person visits including the first in-person MRI scan). For those receiving the MBSR intervention, there will also be four monthly follow-up visits which may be administered in-person or virtually. The one at the conclusion of MBSR training may be combined with scan 2. The MBSR visits are optional, and as long as one visit is completed, the other visits if missed will not result in a deviation.

We hypothesize that teens who vape will differ from those who do not on all behavioral, cognitive and imaging measures and that the MBSR intervention will alter these measures in the vaping teens so that they will differ less from their non-vaping counterparts.

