8.1.2 Screening activities performed after a consent for screening has been signed

At the first visit, after consent/assent is obtained, the following measures will be gathered to further assess eligibility for the study:

Diagnostic Assessment (~1.5 hours)

- a. Clinical history – clinician review
- b. Mini International Neuropsychiatric Interview for Children and Adolescents-DSM-5.0 version (MINI-KID-5) or SCID-RV
- c. MRI Safety Assessment
- a. Substance Use History
 - General Substance Use History Questionnaire (with tobacco & e-cigarette smoking, alcohol, and cannabis questions included)
 - Cannabis Use Disorder Test (CUDIT, 8 items, ~1-2 min)

8.2 Study Evaluations & Procedures after eligibility has been determined.

Administration of questionnaires, interviews, or other instruments (Table 1).

Abbreviated Title: Mindfulness and Teen Vaping

Version Date: 07/21/2025

NIH IRB#: IRB001855

The consent, screening activities listed in 8.1.2, and the baseline assessments listed below may be completed in the same visit virtually or in-person, and all or some of these procedures may also be completed in the same visit as the first scan session. Some questionnaires may be completed virtually in between the consent appointment and Scan Day 1.

Orientation and Initial Baseline Assessments (Visit(s) 1, may be conducted virtually) (~35-55 min):

Demographics and Puberty (~2-5min)

- a. Demographics questionnaire
- b. Pubertal Development Scale

Substance Use Measures

- a. General Substance Use (all participants)
 - Timeline Follow-back (TLFB)
 - Past 28-days tobacco vaping (vaping days and vapes or puffs/day), tobacco smoking, cannabis, alcohol, other drugs if relevant. 7-day TLFB for later visits for vaping teens.
 - Craving Questionnaire (~1-5 min)
- b. E-Cigarette Measures (Vapers only)
 - E-cigarette Dependence Scale (EDS, 4 items, 1 min)
 - Nicotine Social Influence Questionnaire (NSIQ, 1 min)
 - Social influence - peer and family e-cigarette use and approval
 - Modified E-Cigarette Fagerstrom Test for Nicotine Dependence (FTND, 8 items, 1-2 min)

Psychological Measures

- Sensitivity to Reward and Sensitivity to Punishment Questionnaire (SRSPQ, 48 items, 5 min)
- Patient Health Questionnaire-9 (PHQ-9, 9 items, 2 min)
 - Assesses degree of depression severity
- General Anxiety Disorder-7 (GAD-7, 7 items, 2 min)
- Difficulty in Emotion Regulation Scale (36 items, 4 min)
- 5-trial Adjusting Delay Discounting Task (bench, 2 min)

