Within three weeks of the MBSR training completion, vaping participants will complete substance use questionnaires, psychological assessments, mindfulness measures, and cognitive assessments in-person or via secure video call. Our goal is to complete both scan 2 and the initial post-MBSR training assessments within about 1 week after MBSR training. This first follow up visit may be combined with the post MBSR scan 2 but scan 2 may take place as late as approximately 6 weeks after MBSR training to accommodate scheduling. Participants will then have three more follow-up visits, approximately a month apart, in which they complete the measures listed above. These three monthly visits will be dated from the completion of the first assessments following MBSR training (not the scan 2 date). Note: The Digit Span will only be completed at one of the follow up visits, and the FFMQ, DERS and SRSPQ will be completed during two of the visits, preferably the first and the last. The Delayed Discounting questionnaire will only be completed if the follow up visit is in-person. A nursing evaluation consisting of urine sample for a drug test, and breath CO and alcohol test will be taken at each in-person follow-up.

Participants will also engage with the Craving-to-Quit app to elucidate changes in vaping behavior, emotion, and cognition in the 3 months following the MBSR training. The follow-up visits will take about 1 hour each to complete.

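### A vaper whose follow-ups are all virtual and whose scan 2 is a separate visit gets no post-MBSR delay discounting score, despite being on site for that scan

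*Combined protocol and SAP*

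**What the plan says.** **Endpoint.** Section 3 lists as a secondary endpoint "Engagement with apps and Δ scores for each behavioral measure" in vaping adolescents. Section 9.4.2 repeats the plan for change scores on each behavioural measure, and Section 9.4.1 tests pre-post change in continuous measures with paired t-tests.

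**When the task is given.** The 5-trial delay discounting task, put at 2 minutes, is among the baseline assessments of Section 8.2, under the heading "Orientation and Initial Baseline Assessments (Visit(s) 1, may be conducted virtually". After MBSR, Section 8.2 (Follow-up Assessments) restricts it: "The Delayed Discounting questionnaire will only be completed if the follow up visit is in-person".

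**The two tables in Section 1.3.** The Table 1 row reads "5-trial Adjusting Delay Discounting Task (bench), Momentary Impulsivity Scale | X | | | X". Its four visit columns are Visit 1, Visits 2-10, Visit 11 and Visits 12-15, so Visit 11 is blank. The Schedule of Activities row reads "Questionnaires | - | X | - | X | X". Its columns are pre-screening, Visit 1, Visits 2-10, Visit 11 and Visits 12-15, so Visit 11 is marked.

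**Visit mode.** Section 4.1 provides for "four monthly follow-up visits which may be administered in-person or virtually". The note to Table 1 prefers in-person follow-up but allows virtual visits. It adds: "Visit 11 may be combined with Visit 12 or 13 or done separately". Scan visits take place at the research centre (Section 8.2, MRI Sessions).

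**Analysis set.** Under Section 9.3 a vaper needs both scans for the pre-post imaging comparison. With at least one follow-up visit as well, of no stated mode, that vaper joins the assessment of MBSR on vaping and related outcomes.

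**The concern.** A change score needs a value before and a value after. Membership of the outcome set does not depend on visit mode, but having a post-MBSR discounting value does. The plan can therefore count a teen as analysable and still have no discounting change for that teen. It states no rule for the missing score. The one post-MBSR visit that every member of the outcome set must attend in person is scan 2, and Table 1 does not place the task there.

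Two things are at stake. Pairs may be lost, and those remaining may differ from those lost, because missingness is tied to how the visits were held. In addition, where a post value exists, its timing is set by which follow-ups happened to be in person. The first follow-up is within three weeks of MBSR and three more come about a month apart. The change score could therefore mix values from soon after training with values about three months later, after a period of Craving-to-Quit app use.

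**Working it through.** The plan states no figure for delay discounting, so there is none to reproduce. The sample size text in Section 9.2 concerns fMRI only. The main check is a comparison of text; the arithmetic illustrates scale.

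**Step 1: is the path without a score permitted?**
- All of Visits 12-15 virtual: allowed by Section 4.1 and the note to Table 1.
- Scan 2 not combined with a follow-up: allowed by the same note.
- Task at a virtual follow-up: not given, by Section 8.2.
- Task at Visit 11 as a stand-alone visit: not listed in Table 1.
- In the outcome set: yes under Section 9.3, with both scans and at least one follow-up.
- On site after MBSR: yes, for scan 2.

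Both conditions, all follow-ups virtual and scan 2 separate, are needed. One in-person follow-up, or a scan 2 combined with Visit 12 or 13, gives a post value under the existing rule.

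**Step 2: how large could the loss be?**

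Inputs:
- 40 vapers with complete data (Section 4.1).
- Share meeting both conditions: not in the documents; 10, 30 and 50% assumed.
- Standardised mean change d = 0.45: assumed. It is close to the smallest change that 40 pairs detect with 80% power (0.454).
- Two-sided alpha 0.05: assumed.

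Pairs left: n = 40 × (1 − share). Power of the paired t-test: the probability that a noncentral t with n − 1 degrees of freedom and noncentrality d√n falls outside ± the 97.5% point of t with n − 1 degrees of freedom.

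| Share affected | Pairs lost | n | d√n | Critical t | Power |
|---|---|---|---|---|---|
| 0% | 0 | 40 | 2.846 | 2.023 | 0.79 |
| 10% | 4 | 36 | 2.700 | 2.030 | 0.75 |
| 30% | 12 | 28 | 2.381 | 2.052 | 0.63 |
| 50% | 20 | 20 | 2.012 | 2.093 | 0.48 |

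Put the other way, the change detectable with 80% power rises from 0.454 SD at n = 40 to 0.660 SD at n = 20.

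**Step 3: what does collection at Visit 11 change?** Everyone in the outcome set has completed scan 2, so everyone with a baseline value would also have a post value. Loss due to visit mode goes to zero within that set.

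**The case against.** The plan already leans against the problem. In-person follow-up is preferred, scan 2 can be combined with Visit 12 or 13, and Section 8.2 aims to complete scan 2 and the first post-MBSR assessments within about a week of training. This stands as a limit on how often the gap will occur. It does not close the gap, because nothing requires an in-person follow-up or a combined visit, and scan 2 may come as late as about 6 weeks after training.

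The Schedule of Activities marks questionnaires at Visit 11, and Section 8.2 calls this instrument a questionnaire, so staff might give it then anyway. That also stands: the tables are ambiguous for all the psychological measures, not only this one. The ambiguity is itself a reason to reconcile them.

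The task is labelled as a bench task in Table 1, which may explain the in-person rule, although no reason is stated. Giving it at scan 2 respects that rule.

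The measure is minor. It is not named in the outcome table of Section 9.4.3 and becomes an endpoint only through the general wording on each behavioural measure, in a study that calls itself a small pilot. This is correct and sets the priority. Loose timing is not unique to it either: Digit Span is done at one unspecified follow-up.

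A reader might infer that every teen followed virtually lacks a change score, or that the estimate is biased because those who travel in are more engaged. The documents support neither. The loss needs both conditions together, and nothing links visit mode to engagement; distance or scheduling could equally explain it.

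**Conclusion.** The concern holds in a limited form. The written rules permit a vaper to be in the outcome set, and on site after MBSR, with no post-MBSR delay discounting value. For the rest, the timing of the post value follows visit mode. This is a stated rule that can lose data, not a missing detail.

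The size is unknown. The losses of 4, 12 or 20 pairs and the power of 0.75, 0.63 or 0.48 against 0.79 rest on assumed shares and an assumed effect. They should not be read as the expected loss, and the plan claims no power for this measure. Non-random missingness is a possibility only. The point applies to the behavioural outcome set; the baseline comparison of vaping with non-vaping teens needs only scan 1 and is not affected. Priority is low: worth making because it is cheap, not because a main conclusion depends on it.

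**What to change.** 1. In Section 1.3, reconcile the Schedule of Activities with Table 1 on which measures are given at Visit 11, and mark delay discounting there.
2. In Section 8.2 (Follow-up Assessments), state that the task is given in person at Visit 11 to every vaper, whether or not that visit is combined with a follow-up.
3. In Section 9.4, define the pre-post change in delay discounting as Visit 11 minus baseline. Keep any in-person follow-up values as additional time points, and report the number of pairs.

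If Visit 11 collection is not wanted, the minimum is to state that the change score is analysed only in teens with an in-person value and to report how many there are. That discloses the gap but does not close it.

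**Cost.** Two minutes at an existing visit, plus wording. The downside is alignment: Visit 11 may be up to about 6 weeks after MBSR, whereas the other psychological measures are first taken within three weeks, so the discounting change may not match them exactly in time.

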8.2.1 Biospecimen Evaluations

The following biospecimen tests will be collected at scan 1 (Visit 1), scan 2 (Visit 11), and follow-up visits (12-15) to measure nicotine, THC, alcohol, and other drug use.

- Urine Cotinine Test, Urine Drug Test (UDT)
- Breath CO and ALC test

Urine samples acquired for measurements of pregnancy and drug usage at each visit will be destroyed once valid assays have been obtained.

8.2.2 Samples for Genetic/Genomic Analysis

N/A

8.2.2.1 Description of the scope of genetic/genomic analysis

8.2.2.2 Description of how privacy and confidentiality of medical information/biological specimens will be maximized

8.2.2.3 Management of Results

8.2.2.4 Return of Secondary Genomic Research Results

Abbreviated Title: Mindfulness and Teen Vaping

Version Date: 07/21/2025

NIH IRB#: IRB001855

8.2.2.5 Genetic counseling

N/A

8.3 Safety Assessments

Pre-scan assessments:

- Medical update (e.g., height, weight, change in previously provided history, etc.)
- MRI Safety Screen
- Pregnancy test (females of childbearing potential)

Post-scan assessments:

- Assess for wellbeing

No results will be discussed with participants unless something requires referral for medical follow-up.

Safety monitoring: At each scan visit to NIDA, participants are queried about their general medical and emotional health (including current medications and drug use history) since their last visit to NIDA and are observed throughout each visit at NIDA by study investigators. Any change in health status is noted by protocol staff and evaluated for relevance to the participant's participation. Study staff will communicate with participants during the scan and any who want to terminate the scan for any reason will be allowed to. Investigators will refer the participant to the MAI for any medical adverse events or questions about recent medical conditions.

8.4 Adverse Events and Serious Adverse Events

8.4.1 Definition of Adverse Event

Consistent with the Common Terminology Criteria for Adverse Events (CTCAE), an adverse event (AE) is any unfavorable and unintended sign (including an abnormal laboratory finding), symptom, or disease temporally associated with the use of a medical treatment or procedure that may or may not be considered related to the medical treatment or procedure. Severity of each AE (grading) will be determined consistent with the Common Terminology Criteria for Adverse Events (CTCAE) version 5.0.

8.4.2 Definition of Serious Adverse Events (SAE)

A Serious Adverse Event is any Adverse Event that:

- Results in death;
- Is life-threatening (places the subject at immediate risk of death from the event as it occurred);
- Results in inpatient hospitalization or prolongation of existing hospitalization;
- Results in a persistent or significant disability/incapacity;
- Results in a congenital anomaly/birth defect; OR
- Based upon appropriate medical judgment, may jeopardize the subject's health and may require medical or surgical intervention to prevent one of the other outcomes listed above in this definition (examples of such events include allergic bronchospasm requiring intensive treatment in the emergency room or at home, blood dyscrasias or convulsions

Abbreviated Title: Mindfulness and Teen Vaping
Version Date: 07/21/2025
NIH IRB#: IRB001855

that do not result in inpatient hospitalization, or the development of drug dependency or drug abuse).

An adverse event (AE) or suspected adverse reaction is considered “serious” if, in the view of either the investigator or sponsor, it results in any of the following outcomes: death, a life-threatening adverse event, inpatient hospitalization or prolongation of existing hospitalization, a persistent or significant incapacity or substantial disruption of the ability to conduct normal life functions, or a congenital anomaly/birth defect. Important medical events that may not result in death, be life-threatening, or require hospitalization may be considered serious when, based upon appropriate medical judgment, they may jeopardize the participant and may require medical or surgical intervention to prevent one of the outcomes listed in this definition. Examples of such medical events include allergic bronchospasm requiring intensive treatment in an emergency room or at home, blood dyscrasias or convulsions that do not result in inpatient hospitalization, or the development of drug dependency or drug abuse.

